5.1. Disposition

A summary of the analysis populations will include the number and percentage of participants for the following categories: participants in the Screened population, Screen Failures, Safety population, PD Evaluable population (if applicable), and PK Evaluable population. All percentages will be based on the number of participants in the Screened population. Screen failures will be defined as participants who consent to participate in the clinical study but are not subsequently administered study drug (i.e., are not part of the Safety Population).

A disposition of participants will include the number and percentage of participants in the Safety population for the following categories: participants who completed the study or discontinued early, as well as the reasons for discontinuation.

A summary of the participants excluded from PD Evaluable (if applicable) and PK Evaluable analysis population and the reasons for exclusion will be presented. Percentages for exclusion reasons will be based on the number of participants excluded from the specific analysis population being summarized. Participants could be excluded from an analysis set for more than one reason.

Disposition data will be presented in a listing for the Safety population.

5.2. Protocol Deviations

Major protocol deviations will be identified and documented based on review of protocol deviations before database lock, and will be used to define the PD Evaluable Population (if applicable). The categories of major protocol deviations to be reviewed include, but are not limited to, participants who:

- Did not meet key inclusion/exclusion criteria in the judgment of the evaluability committee
- Received disallowed concomitant medication that could meaningfully impact results
- Had overall treatment compliance rate <80% or >120%

The number and percentage of participants with major protocol deviations will be summarized for the Safety Population by type of deviation. All protocol deviations will be presented in a data listing.

6. Demographics and Baseline Characteristics

6.1. Demographics

A summary of demographics and baseline information will be presented. The demographic characteristics consist of age (year), sex, race, and ethnicity. The baseline characteristics consist of baseline height (cm), baseline weight (kg), and baseline body mass index (BMI) (kg/m²). Body mass index is calculated as (body weight in kilograms) / (height in meters)².

A participant's age in years is calculated using the date of the informed consent and date of birth. Age (year), baseline height (cm), baseline weight (kg), and baseline BMI (kg/m²) will be summarized using descriptive statistics. The number and percentage of participants by sex (Male, Female), race (White, Black or African American, Asian, American Indian or Alaska Native, Native Hawaiian or Other Pacific Islander, and Other) and ethnicity (Hispanic or Latino, Not Hispanic or Latino), will also be reported. Percentages will be based on the total number of participants in the Safety population.

Participant demographic and baseline characteristics will be presented in a listing for the Safety population.

6.2. Drug and Alcohol Screen

Drug and alcohol screening test will be conducted as scheduled in **Table**. Test results will be presented in a listing for participants in the Safety population.

6.3. Smoking History

Smoking history will be presented in a listing for participants in Safety population. It includes the following categories: Smoking Status (Current, Previous, Never), Type of Tobacco Substance (Cigarettes, Cigars, Pipes, Chewing Tobacco, Vaping (e-cigarette)), start date /end date and number of uses per day.

6.4. Medical History

6.4.1. General Medical History

The number and percentage of participants with any medical history will be presented by system organ class (SOC) and preferred term (PT). At each level of summarization, a participant will be counted once if the participant reported one or more events. The

summary will be presented alphabetically by SOC and within each SOC, by decreasing total incidence of PT. If the incidence for any two or more PTs is equal, the PTs will be presented in alphabetical order. . Body systems will be included as recorded on the electronic case report form (eCRF). Percentages will be calculated based on the number of participants in the Safety population.

Medical history data will be presented in a listing for participants in the Safety population.

7. Treatments and Medications

7.1. Prior and Concomitant Medications

All medications that the participant is receiving at the time of Screening until the Follow-up Visit will be collected on the case report form (CRF). All medications will be coded according to the World Health Organization drug dictionary (WHODRUG 2019 Mar).

Prior medication will be defined as any medication with the start date prior to the date of the first dose of the investigational product. Concomitant medication will be defined as any medication with a start date prior to the date of the first dose of study drug and continuing after the first dose of study drug or with a start date between the dates of the first dose of study drug and the follow up visit date, inclusive. Incomplete medication dates will be imputed as described in Section 16.3.

Prior and concomitant medication use will be summarized for the Safety Population by the number and percentage of participants receiving each medication within each therapeutic class. Multiple medications used by a participant in the same category (based on Anatomical-Therapeutic-Chemical classification) will be counted only once. All prior and concomitant medications will be presented in a listing for participants in the Safety population.

7.2. Study Treatments

All eligible participants will receive open-label IW-6463 at a starting dose of 15 mg QD. The appropriate amount of study drug will be dispensed to participants on Day 1 of the Treatment Period. Drug will be resupplied as needed. Participants will be asked to record the date and time of each at-home study drug administration in their daily diary; these diaries will be checked for dosing compliance at each scheduled visit during the Treatment Period.

Participants will be asked to bring their study drug supply and daily diary to each in-clinic visit during the Treatment Period.

7.2.1. Extent of Exposure

Duration of exposure is defined as the total number of days a participant is exposed to any study drug and will be presented as the total number of days from the first dose date (Day 1) to the last dose date (date of last dose minus the date of first dose + 1) as recorded on the exposure page on the CRF. The duration of exposure to study drug will be summarized for all participants in the Safety population and will be presented in a table by summary statistics.

The total number of doses taken for the entire study will be calculated and summarized for all participants in the Safety population and will be presented in a table by summary statistics.

Each participant's study drug administration information will be presented in a listing.

7.2.2. Treatment Compliance and Modifications

Compliance is defined as the total dosage taken divided by the total dosage expected to be taken, times 100. The treatment compliance will be summarized for all participants in the Safety population. Compliance rates will also be categorized as missing, <80%, ≥80% and ≤120%, and >120% and will be summarized. Overall compliance will be listed for all participants in the Safety population.

8. Efficacy Analysis

Not applicable.

9. Safety Analysis

If not otherwise specified, the safety analyses will be performed using the Safety population. If not otherwise specified, the baseline value is defined as the last non-missing value measured (scheduled or unscheduled measurements) before administration of study drug on Day 1.

If there is more than 1 safety measurement (e.g., for a lab endpoint) at a postbaseline timepoint, only the last measurement will be used for by visit summary. All postbaseline assessments including unscheduled assessments, if any, will be used for shift tables, and all assessments will be presented in listings.

A listing of all participants affected by the coronavirus disease (COVID-19) related study disruption will be presented for participants in Safety population.

9.1. Adverse Events

Adverse events will be coded using MedDRA Version 24.0.

Pretreatment AEs are defined as AEs with a start date between the informed consent date and the date of the first dose of study drug.

Treatment-emergent AEs are defined as AEs reported in the clinical database with a start date on or after the first dose of study drug until the end of the follow-up period.

An overall summary of the number of participants in the Safety population with AEs will be presented, including the number and percentage of participants with AEs, pretreatment AEs, TEAEs, severe TEAEs, drug-related TEAEs, serious AEs, AEs leading to death, TEAEs leading to study drug discontinuation and Treatment-emergent adverse events of special interest (AESIs).

All AEs will be presented in listings for the Safety population, and AEs will be flagged to denote pretreatment AEs and TEAEs. Incomplete AE start dates will be imputed as described in Section 16.2.

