3. OBJECTIVES AND ENDPOINTS

Objective	Endpoint
Primary:	

 To evaluate the safety and tolerability of IW-6463 when administered to participants with MELAS 	
 Number of participants with study drug dose reductions or discontinuations due to ≥ 1 TEAE Incidence and severity of AEs
Exploratory:	

 To evaluate the PK of IW-6463 when administered to participants with MELAS 	
 Plasma and CSF concentrations of IW-6463 as data permit, at assessed timepoints PK parameters as data permit, including but not limited to AUC_{tau}, T_{max}, $t_{1/2}$, C_{max}, C_{trough}, CL/F, V_z/F, and the CSF:plasma concentration ratio

 To evaluate the effect of IW-6463 on exploratory plasma biomarkers in participants with MELAS 	
 Change from baseline in plasma biomarker concentrations on Day 29 *

 To evaluate the effect of IW-6463 on CBF in participants with MELAS 	
 Change from baseline in CBF as measured by ASL on Day 29

 To evaluate the effect of IW-6463 on brain activity as measured by fMRI in participants with MELAS 	
 Change from baseline in fMRI-BOLD signals during resting state and a visual stimulus on Day 29, as data permit

 To evaluate the effect of IW-6463 on brain metabolites as measured by MRS 	
 Change from baseline in brain metabolite [REDACTED] levels by ^1H-MRS on Day 29

 To evaluate the effect of IW-6463 on fatigue as measured by the MFIS 	
 Change from baseline in MFIS scores (total, physical, cognitive, and psychosocial subscores) on Day 29

 To evaluate the effect of IW-6463 on cognitive function as measured by the PROMIS Item Bank v2.0—Cognitive function 	
 Change from baseline in PROMIS Item Bank v2.0—Cognitive function total score on Day 29

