9.3.8. Safety Analyses

Incidence of AEs will be summarized by Medical Dictionary for Regulatory Activities system organ class and preferred term. By-participant listings will be provided for pretreatment AEs, TEAEs, severe AEs, drug-related AEs, SAEs, and AEs leading to study discontinuation or death. All safety analyses will be conducted on the Safety Population.

ECGs, vital signs, and clinical laboratory tests (in International System [SI] units) at each assessment time point and the change from baseline at each postbaseline time point will be summarized using descriptive statistics unless noted otherwise. Listings will be provided for participants with abnormal values.

A TEAE is defined as an adverse event that emerges during treatment, having been absent pretreatment, or that worsens relative to the pretreatment state.

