10.2.1.1. Definition of TEAE

A TEAE is defined as an adverse event that emerges during treatment, having been absent pretreatment, or that worsens relative to the pretreatment state.

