9.1.1. Dose Reductions or Discontinuations due to TEAE

The number and percentage of participants with study drug dose reductions, or with study drug discontinuations due to TEAE (that is, participants who have a TEAE with a study treatment action taken of “Dose Reduced” or “Drug Withdrawn”) will be summarized for participants in the Safety population. A participant will be counted once if they experienced both these events. Percentages will be calculated based on the number of participants in the Safety population.

All TEAEs lead to study drug dose reductions or study drug discontinuations will be presented in a listing for the Safety population.

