9.1.4. Relationship of Adverse Events to Study Drug

A summary of TEAEs by relationship (“Related” and “Unrelated”) to study drug per investigator will be presented by SOC, PT, and relationship in a manner similar to that described in Section 9.1.1. Percentages will be calculated based on the number of participants in the Safety population.

If a participant reported more than 1 TEAE within an SOC or PT, then the TEAE with the strongest causality relationship to study drug per investigator within each SOC and each PT will be included. If the relationship to study drug is missing for a TEAE, all efforts should be made to obtain the relationship from the Investigator. If it is still missing after all efforts, a study drug causality of “Related” will be assigned for TEAEs. The imputed values for the missing relationship to study drug will be used only for incidence summary, while the actual missing values will be presented in listings.

All drug-related AEs will be presented in a listing for the Safety population, and AEs will be flagged to denote pretreatment AEs and TEAEs.

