9.1.5. Serious Adverse Events

Serious TEAE will be presented by SOC and PT in a manner similar to that described in Section 9.1.12. Percentages will be calculated based on the number of participants in the Safety population.

All participants in the Safety population who have an SAE will be presented in a listing and AE will be flagged to denote pretreatment AEs and TEAEs.

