9.1.6. Adverse Events Leading to Study Drug Discontinuation

A summary of study drug discontinuations due to TEAE (that is, participants who have a TEAE with a study treatment action taken of “Drug Withdrawn”) will be presented by SOC and PT in a manner similar to that described in Section 9.1.1. At each level of participant summarization, a participant is counted once if the participant reported one or more events. Percentages will be calculated based on the number of participants in the Safety population.

All participants in the Safety population who have an AE leading to study drug discontinuations or an AE leading to study discontinuation (that is, participants who answer “Yes” to the question of “Caused Study Discontinuation”) will be presented in a listing and AEs will be flagged to denote pretreatment AEs and TEAEs.

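### SAP 9.1 defines a TEAE by start date alone and drops, without declaring it, the protocol's worsening criterion, so the first primary endpoint can be undercounted.

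*SAP*

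**What the plan says.** Protocol 10.2.1.1 reads: "A TEAE is defined as an adverse event that emerges during treatment, having been absent pretreatment, or that worsens relative to the pretreatment state". Protocol 9.3.8, the statistical section on safety, repeats the definition, including "or that worsens relative to the pretreatment state".

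SAP 9.1 reads: "Treatment-emergent AEs are defined as AEs reported in the clinical database with a start date on or after the first dose of study drug", with the window running to the end of follow-up. The same section classes any AE that starts between consent and first dose as pretreatment. Nothing in the SAP reclassifies such an AE if it later gets worse.

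The first primary endpoint (Protocol 3, SAP 3.2.1) is the "Number of participants with study drug dose reductions or discontinuations due to" one or more TEAEs. SAP 9.1.1 derives it from participants who have a TEAE whose action taken is a dose reduction or drug withdrawal. Its supporting listing has the same restriction: "All TEAEs lead to study drug dose reductions or study drug discontinuations will be presented in a listing for the Safety population".

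Other tables also rest on TEAE status. SAP 9.1.4 plans "A summary of TEAEs by relationship", and SAP 9.1.5 states "Serious TEAE will be presented by SOC and PT". The SAP 9.1.6 table of drug discontinuations is limited to TEAEs, but its listing takes any AE and "will be presented in a listing and AEs will be flagged to denote pretreatment AEs and TEAEs".

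**The concern.** Two documents governing the same analysis give different rules for the event that defines a primary endpoint. SAP Section 14 lists eight changes or clarifications relative to the protocol, some as small as listing all deviations rather than major ones only. The TEAE definition is not among them.

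AEs are collected from consent (Protocol 4.1.1), and Screening falls 10 to 28 days before dosing, so pre-dose AE records can exist in treated participants. If one of these AEs worsens on drug and causes a dose reduction or withdrawal, it bears directly on tolerability, the study's primary question. Under the SAP it can be absent from the tolerability count. On this point the error runs one way: the SAP count can equal the protocol count or fall below it, never exceed it.

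**Working it through.** No figure in the plan needs reproducing, because the endpoint is a simple count. The check applies each definition to the same events and then sizes the difference.

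**1. The two rules on three example AEs** (Day 1 = first dose)

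| AE | Protocol | SAP 9.1 |
|---|---|---|
| Starts Day 3 | TEAE | TEAE |
| Starts Day -10, does not worsen | Not a TEAE | Not a TEAE |
| Starts Day -10, worsens Day 5, same record kept | TEAE | Pretreatment AE |

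The rules differ only in the third row.

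**2. Is a new record required at worsening?** If it were, the start date would fall on drug and the SAP rule would capture the event. The documents give no general rule. Protocol 8.3.2 (examination findings) and 10.1 (laboratory values) call for an AE only when the change is not already part of an ongoing one. These cover only two kinds of finding, and if anything they favour keeping the existing record. SAP 16.2 deals only with incomplete or missing start dates and does not help when the date is complete.

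**3. Where the event goes if the pre-dose record is kept**

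- Absent from: the 9.1.1 count and listing; the 9.1.4 relationship table; the 9.1.5 serious-TEAE table; the 9.1.6 discontinuation table.
- Shown as pretreatment in: the 9.1.2 incidence and 9.1.3 severity tables, which serve the second primary endpoint. SAP 9.1.3 also imputes a missing severity as mild for a pretreatment AE and severe for a TEAE, so the class can change the severity shown.
- Still visible in: the all-AE listing and, for a withdrawal, the 9.1.6 listing. A dose reduction has no dedicated listing other than the TEAE-only one in 9.1.1.

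**4. Size per affected participant.** The expected Safety Population is about 20 (Protocol 4.3). N = 12 is an assumption for a smaller study; SAP 4.3.3 provides for the possibility that fewer than 12 enrol. Limits are exact (Clopper-Pearson) 95%: lower = Beta(0.025; x, n-x+1), upper = Beta(0.975; x+1, n-x).

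| N | One participant | Counted | Missed |
|---|---|---|---|
| 20 | 1/20 = 5.0 points | 1/20 = 5.0% (0.1 to 24.9) | 0/20 = 0% (0 to 16.8) |
| 12 | 1/12 = 8.3 points | 1/12 = 8.3% (0.2 to 38.5) | 0/12 = 0% (0 to 26.5) |

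**5. Chance of at least one miss.** The documents give no event rate. Suppose a fraction p of participants has such an event, leading to reduction or withdrawal and kept on its pre-dose record. Then P(at least one) = 1 - (1 - p)^N:

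| Assumed p | N = 20 | N = 12 |
|---|---|---|
| 2% | 33.2% | 21.5% |
| 5% | 64.2% | 46.0% |
| 10% | 87.8% | 71.8% |

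**6. Exposed window.** From Protocol 4.6, at most 28 of 28 + 29 + 18 = 75 days precede dosing: 28/75 = 37.3%. This is a share of calendar time, not a risk.

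**The case against.** The strongest reply is that the loss depends on material outside these documents. If the eCRF completion guidelines require a new record when an AE worsens, the start-date rule captures the event and the two definitions agree in practice. The case is also narrow: the AE must begin after consent, persist through the Day 1 checks, worsen on drug, lead to reduction or withdrawal, and stay on its old record. Symptoms already present at consent are medical history; if first reported as an AE on drug with an on-drug start date, they are captured either way.

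With about 20 open-label participants, such a case would probably be noticed. Besides the listings named above, SAP 9.1.4 lists all drug-related AEs, SAP 9.1.5 lists all SAEs, and SAP 7.2.1 lists drug administration, where a dose change should be traceable. The pretreatment flag in the 9.1.6 listing is standard wording found in several listings, so it does not show that the authors foresaw this case. The SAP's modification history covers changes between SAP versions, so its silence is weak evidence; Section 14 is the relevant place. The SAP plans no confidence interval for this endpoint, so the intervals above are illustrative.

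All of this limits the likely size. It does not remove the contradiction: listings do not correct a primary count, and a recording rule that the plan depends on should be stated.

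**Conclusion.** The concern holds and should be fixed. The mismatch between SAP 9.1 and Protocol 9.3.8 and 10.2.1.1 is clear on the text, Section 14 does not declare it, and it feeds straight into the first primary endpoint. As written, the two documents can give different counts from the same data, with the SAP count the lower. Each affected participant is worth 5.0 percentage points at 20 treated and 8.3 at an assumed 12.

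The undercount itself is conditional: it requires at least one qualifying event, and that its worsening stays on the pre-dose record. The frequency is unknown. The second primary endpoint keeps the event but shows it as pretreatment.

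**What to change.** In SAP 9.1, define a TEAE as an AE with onset at or after first dose through Follow-up, or with earlier onset and an increase in severity or seriousness at or after first dose. State how worsening is captured: a new record, or a dated severity change on the existing one. Carry the definition through 9.1.1 to 9.1.8, so that the tables, the listing flags and the treatment-emergent AESI count agree. Keep 9.1.1 limited to TEAEs, as the protocol endpoint requires.

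If the date-only rule is intended, declare it in Section 14 with a reason and reconcile it with Protocol 9.3.8 and 10.2.1.1.

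The cost is SAP wording and a one-line eCRF completion instruction, with no new assessments. A dated severity change might need an extra eCRF field if none exists; the new-record route would not.

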9.1.1. Dose Reductions or Discontinuations due to TEAE

The number and percentage of participants with study drug dose reductions, or with study drug discontinuations due to TEAE (that is, participants who have a TEAE with a study treatment action taken of “Dose Reduced” or “Drug Withdrawn”) will be summarized for participants in the Safety population. A participant will be counted once if they experienced both these events. Percentages will be calculated based on the number of participants in the Safety population.

All TEAEs lead to study drug dose reductions or study drug discontinuations will be presented in a listing for the Safety population.

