4.1.2. Treatment Period

The Treatment Period begins on Day 1 (there is no "Day 0") when participants return to the Study Center to undergo baseline procedures and receive their first daily dose of study drug. Participants will return to the Study Center on Day 29 (-4 days) for the End-of-Treatment (EOT) Visit; all other scheduled visits during this period will be completed within the allowable timeframe either at home or in the study center, per participant preference. Throughout the Treatment Period, participants will continue completing their daily diary (see Section 8.4).

The end of the Treatment Period coincides with the beginning of the Follow-up Period.

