4.6. Duration of Individual Participation

The overall study duration per participant will be a maximum of 75 days, including the Screening (≤ 28 days), Treatment (≤ 29 days), and Follow-up (≤ 18 days) periods.

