6.2. Dose Adjustment Criteria for Individual Participants

6.2.1. Safety Criteria

The decision to de-escalate IW-6463 dosing in an individual participant will be made jointly by the Investigator and the designated CRO-based Medical Monitor, on a per-participant basis.

Participants who require a dose adjustment from the 15-mg QD dose will be de-escalated to a 10-mg QD dose. Initiation of the new dose level should occur only after the TEAE(s) prompting the dose reduction has/have resolved or has improved to be considered mild in severity.

If the 10-mg IW-6463 QD dose is not tolerated, the participant will be discontinued from study drug. See Section [5.6.2](#) for study drug discontinuation procedures for individual participants.

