3.4. Dose Adjustment/Modifications

The decision to de-escalate IW-6463 dosing in an individual participant will be made jointly by the Investigator and PPD Medical Monitor, on a per-participant basis.

Participants who require a dose adjustment from the 15-mg QD dose will be de-escalated to a 10-mg QD dose. Initiation of the new dose level should occur only after the Treatment-emergent AE(s) prompting the dose reduction has/have resolved or has improved to be considered mild in severity.

If the 10-mg IW-6463 QD dose is not tolerated, the participant will be discontinued from study drug.

4. General Statistical Considerations

Continuous variables will be summarized using the following descriptive statistics: n, mean, median, standard deviation, minimum, maximum. For the summary of continuous clinical outcomes, vital signs, and PD data, the 95% confidence intervals (CI) will also be presented. For the summary statistics of all numerical variables, unless otherwise specified, minimum and maximum will be displayed to the same level of precision as reported. Mean and median will be displayed to one level of precision greater than the data collected. Standard deviation will be displayed to two levels of precision greater than the data collected.

Categorical and count variables will be summarized by the number of participants (n) and the percent of participants in each category. Percentages will be presented as whole numbers. When count data are presented, the percentage will be suppressed when the count is zero. A row denoted “Missing” will be included in count tabulations only if there are missing values. The denominator for all percentages will be the number of participants within the population of interest, unless otherwise specified.

Baseline will be defined as the last non-missing assessment before administration of study drug on Day 1, unless otherwise specified.

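### SAP 9.1.1 derives the first primary endpoint from two AE action codes alone, so a TEAE-driven stop that is never restarted can be missed if it is coded any other way

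*SAP*

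**What the plan says.** Protocol section 3 gives the first of two primary endpoints as "Number of participants with study drug dose reductions or discontinuations due to ≥ 1 TEAE". The second is the incidence and severity of AEs.

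SAP 9.1.1 puts the first endpoint into operation. It summarises participants "with study drug dose reductions, or with study drug discontinuations due to TEAE" and adds that these are participants with a TEAE whose study treatment action was 'Dose Reduced' or 'Drug Withdrawn'. Each participant counts once, and the denominator is the Safety population. SAP 9.1.6 uses 'Drug Withdrawn' alone. Neither document mentions a dose interruption or hold as a category.

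The dose-adjustment rule is in Protocol 6.2.1: "Initiation of the new dose level should occur only after the TEAE(s) prompting the dose reduction has/have resolved" or has improved to mild. SAP 3.4 repeats it. Neither text sets a maximum wait, says whether the starting dose continues in the meantime, or says how to classify a participant whose event has not settled when treatment ends. Discontinuation is required only if the lower dose has been tried and not tolerated.

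Time is limited. Protocol 4.6 caps treatment at 29 days, and Protocol 4.1.2 states: "Participants will return to the Study Center on Day 29 (-4 days) for the End-of-Treatment (EOT) Visit".

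**The concern.** A participant judged unable to stay on the starting dose must wait for the event to settle before the lower dose can begin. The natural reading is that this participant is off drug while waiting, although the text does not say so. If the event has not settled by the EOT visit, the lower dose never starts, and no passage then requires a formal withdrawal. Study completion (Protocol 5.6.1) depends on completing the study periods, not on taking drug.

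In substance that participant discontinued because of a TEAE, which is what the protocol endpoint counts. Under the SAP, inclusion depends on the action term entered for the AE, with no check against dosing records. For this count an omission can only lower the result. With about 20 treated participants, one omission is visible in a primary result.

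**Working it through.** **Inputs.** Treatment of up to 29 days and the 75-day maximum (Protocol 4.6); EOT on Day 29, -4 days (Protocol 4.1.2); at most 20 treated and about 12 evaluable (Protocol 9.2, SAP 4.1); the two action codes and the Safety denominator (SAP 9.1.1).

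**The plan's own figures.** The sample size is stated not to rest on statistical considerations, so there is no power calculation to reproduce. The durations agree: 28 + 29 + 18 = 75 days. The total leaves no room to extend treatment for a participant who is waiting.

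**Can the wait outlast treatment?** Days left after the last dose = EOT day minus day of last dose.
- Last dose on Day 8: 29 - 8 = 21 days, or 25 - 8 = 17 if EOT is at the early end of its window.
- Last dose on Day 15: 29 - 15 = 14 days, or 25 - 15 = 10.

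A TEAE that stays moderate or severe for longer than this leaves the participant without a restart.

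**What SAP 9.1.1 does with each outcome.**

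| Course | Action entered | Counted in 9.1.1? | Within protocol endpoint? |
|---|---|---|---|
| Event settles, lower dose starts | Dose Reduced | Yes | Yes |
| Stopped, never restarted | Drug Withdrawn | Yes | Yes |
| Stopped, never restarted | Dose Reduced (decision recorded) | Yes | Yes |
| Stopped, never restarted | Interruption-type term, or left unresolved | **No** | **Yes** |

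Only the last row is a defect. It requires a code, or a blank, that the documents neither show nor exclude.

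**Size of one missed participant.** Proportion = x/n, with exact (Clopper-Pearson) two-sided 95% limits. The SAP does not plan an interval for this endpoint; it is used here only as a gauge. For x = 0 the upper limit is 1 - 0.025^(1/n).
- n = 20: 0/20 = 0% (0 to 16.8%) becomes 1/20 = 5.0% (0.1 to 24.9%).
- n = 12, if only 12 were treated: 0/12 = 0% (0 to 26.5%) becomes 1/12 = 8.3% (0.2 to 38.5%).

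**Chance of at least one TEAE-driven stop never restarted.** The documents give no rate, so the rate p per participant is assumed. Chance = 1 - (1 - p)^n.

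| Assumed p | n = 20 | n = 12 |
|---|---|---|
| 2% | 33% | 22% |
| 5% | 64% | 46% |
| 10% | 88% | 72% |

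These are chances that such a stop occurs. The chance that one is missed is lower, because some would be coded with a term that is counted.

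**The case against.** The strongest reply is that correct coding already solves this. Protocol 10.1 has the investigator report the action taken with study drug for every AE. Protocol 5.6.2 asks for EOT assessments when study drug is discontinued and for the sponsor to be told of any premature discontinuation. A stop that never restarts would naturally be entered as 'Drug Withdrawn', or as 'Dose Reduced' if that decision had been recorded, and both are counted. This stands as far as it goes: the omission is possible, not shown. But the SAP neither defines this case nor checks the code against the doses taken.

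Four stronger readings are tempting, and the documents do not support them.

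- *That the rule creates a dosing hold.* Protocol 6.2.1 restricts only the start of the new dose. The off-drug interval is an inference.
- *That a missed participant is reported as having tolerated the drug.* No such category exists. The participant is absent from one count, while the TEAE stays in the second primary endpoint and in the AE listings.
- *That the exposure table hides the problem too.* SAP 7.2.1 computes duration from first to last dose, so a permanent stop shortens it, and the same section summarises total doses taken. A gap followed by a restart at the lower dose is counted as a reduction. These summaries are not linked to TEAEs, so they do not correct the primary count, but they need no change.
- *That every TEAE-related interruption belongs in the endpoint.* The protocol counts reductions and discontinuations. A participant who paused and returned to the same dose would have neither, and the documents describe no such route. Adding that participant would widen the endpoint.

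**Conclusion.** The concern holds in a limited form. The SAP derivation is narrower than the protocol endpoint for one kind of participant: dosing stopped for a TEAE, no restart before EOT, and an action term other than the two named. Each such participant lowers the reported proportion by 5.0 points with 20 treated, the planned size of the Safety population, or by 8.3 points if only 12 are treated.

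The conclusion rests on two assumptions: that dosing stops during the wait, and that the eCRF permits an interruption-type or unresolved entry. How often this would happen is unknown. A one-directional bias in the primary endpoint is therefore possible but not demonstrated. The change is still worth making, because the endpoint is primary, the numbers are small and the data needed are already collected.

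**What to change.** In SAP 9.1.1:

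1. Count as a discontinuation due to TEAE any participant whose dosing stopped because of a TEAE and who has no further dose recorded up to the EOT visit, whatever action term was entered. Establish the stop and the absence of a restart from the exposure page, checked against the diary, before database lock. Keep the Safety denominator and the count-once rule, and include these participants in the 9.1.1 listing. Apply the same rule in 9.1.6 so that the two tables agree.
2. Show participants with a TEAE-related interruption in a separate supportive row. The protocol-defined endpoint stays as it is.

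The sponsor should reconcile Protocol 6.2.1 and SAP 3.4 with this definition, so that it is clear how a participant who never reaches the lower dose is classified. No dosing rule is proposed, and SAP 7.2.1 needs no change.

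The cost is a few sentences of SAP text, one table row and a programmed cross-check of data already collected. The downside is that the tolerability figure may be slightly less favourable.
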